2.7.2 Known Potential Benefits

Potential participants will have aspects of their health status screened by qualified clinicians. This screening will be free of cost to the participant's family and may provide important health information to the screening candidates.

The study will provide the opportunity for some of the participant to be tested for anti-rotavirus antibodies, a test which is not commonly available. Results will be reviewed with them and shared with their personal physician, if so desired by the participant's parent/LAR.

The information sheet and the physician will educate the family about rotavirus diarrhea and its prevention and treatment.

Protection from rotavirus diarrhea is a possible benefit, although because the vaccine is experimental it cannot be guaranteed. Participants may not benefit personally through study participation. By participating in this study, participants will contribute information on the safety and immunogenicity of this new vaccine against rotavirus in Vietnam. Development of new rotavirus vaccine, such as this new formulation of ROTAVIN-M1, that is locally produced, more stable and potentially less expensive, would be a significant contribution to public health in Vietnam and regionally.

There are no other known potential benefits to the participant for participation in this trial. Given the history of good safety profiles of rotavirus vaccines, the risk-benefit ratio is considered favorable, especially considering that all participants will be under the observation of qualified medical personnel.

3 STUDY OBJECTIVES AND OUTCOME MEASURES

3.1 Study Objectives

3.1.1 Primary Objectives

Immunogenicity

To demonstrate non-inferiority in the immunogenicity of the liquid formulation of ROTAVIN in comparison to currently licensed frozen formulation of the Vaccine (ROTAVIN-M1), 28 days after the last dose of the vaccine when administered to infants in a two-dose schedule starting at 60-91 days of age.

Safety

To evaluate the safety of liquid formulation of ROTAVIN in comparison with currently licensed frozen formulation (ROTAVIN-M1), in terms of solicited reactions after each dose of vaccine.

Confidential
3.1.2 Secondary Objective

Immunogenicity

To further characterize the immunogenicity of the liquid formulation of ROTAVIN in comparison with currently licensed frozen formulation of the Vaccine (ROTAVIN-M1).

Safety

To evaluate the safety of the liquid formulation of ROTAVIN in terms of immediate postvaccination events, unsolicited adverse events and serious adverse events, including monitoring for intussusception.

3.2 Outcome Measures

3.2.1 Primary Endpoint

Immunogenicity

Rotavirus vaccine immunogenicity will be tested on serum samples obtained in a subset of 450 participants before the first vaccination and four weeks after the second vaccination using a validated ELISA assay. The primary immunogenicity endpoint is as follows:

• Geometric mean concentration (GMC) of serum anti-rotavirus IgA antibody concentrations 28 days after the second vaccination.

Safety

Solicited post-vaccination reactogenicity (fever, diarrhea, vomiting, decreased appetite, irritability, and decreased activity level) during the 7 day period (Day 1-7) after each vaccination

3.2.2 Secondary Endpoint

Immunogenicity

- Percentage of participants with seroconversion in serum anti-rotavirus IgA antibody concentrations 28 days after the second vaccination.
- For participants with a negative pre-vaccination IgA concentration (< 20 IU/ml), a positive post-vaccination IgA concentration (\geq 20 IU/ml);
- For participants with a positive pre-vaccination IgA concentration, a post-vaccination IgA concentration at least 4 times as high as the pre-vaccination IgA concentration.
- Percentage of participants with seropositivity at baseline and 28 days after the second vaccination. Seropositivity is defined as serum IgA antibody concentration ≥ 20 IU/ml.

Safety

- Immediate adverse events, within 30 minutes after each vaccination.
- Unsolicited AEs from vaccination through four weeks after each dose.
- Serious adverse events (SAEs) and Intussusception from first vaccination through four weeks after the last vaccination.

4 STUDY DESIGN

The study is designed as a phase III, multicenter, randomized, partially double-blinded, active controlled study enrolling 825 infants 60-91 days of age. The objective of the study is to compare

the safety and immunogenicity of the liquid formulation of ROTAVIN with already licensed vaccine ROTAVIN-M1.

The study will be conducted at commune health centres in Nam Dinh and Quang Ninh provinces in Vietnam. The study visits will be planned in advance such that the EPI vaccination days fall either 7 days before or after the study vaccination day. This will allow the participant to receive EPI vaccines in the window allowed by the protocol. Prospective participants, whose parent or legal guardian sign an informed consent form will be assessed for eligibility to participate in the study. Screening for eligibility will include solicitation of medical history, assessment of vital signs and physical examination. If the participant is found to be eligible, the infants will be allocated to one of the two groups at a ratio of 2:1 to receive the study vaccine with 550 participants receiving the liquid formulation of ROTAVIN and 275 participants receiving the frozen formulation (ROTAVIN-M1). The study will be conducted according to a partially blinded study design in which the vaccine administerer will be considered unblinded whereas the parents, and rest of the study team including endpoint accessor will be blinded to the treatment received by the child. Two doses of vaccine will be administered 8 (+2) weeks apart (minimum interval of 8 weeks and maximum of 10 weeks), with the first administration given at 60-91 days of age (both days inclusive). Childhood vaccines as per the Expanded Program for Immunization of the Government of Vietnam will not be allowed within 7 days before or after study vaccine administration.

To evaluate the Rotavirus vaccine immunogenicity, blood samples will be obtained from all the participating infants from Quang Ninh site before the first and four (+2) weeks after the second vaccination. Immunogenicity will be assessed in all infants who provided blood samples at the selected site. Serum Anti-rotavirus IgA antibodies will be analyzed at Cincinnati Children's Hospital Medical Center (CCHMC), Cincinnati, Ohio, USA using a validated ELISA which uses strain 89-12 as a substrate.

Vaccinated participants will be observed for immediate adverse events for 30 minutes after each vaccination. Active surveillance for vaccine reactogenicity (solicited reactions) over the 7-day period after each vaccination, unsolicited AEs for 4 weeks after each vaccination and SAEs including intussusception over the period between first vaccination and four weeks after the last vaccination will be conducted for all infants.

This protocol will have extensive safety monitoring in place. At the performing site level, the study site investigators and their clinical staff will be responsible for continuous close safety monitoring of all study participants and for alerting the protocol team if unexpected concerns arise. An team of vaccine experts, Safety Review Committee (SRC) composed of a group of physicians which include but not limit to the designated investigator from study team and the Medical Officer(s) from POLYVAC and PATH, a Pharmacovigilance/Medical officer from the CRO and an independent vaccine expert will be closely following the study for safety oversight. The SRC may seek independent expert medical opinion as dictated by the occurrence of certain events.

The SRC will have provision of expedited meeting that could be triggered by reporting of predefined AEs. The SRC may also seek independent expert medical opinion as dictated by the occurrence of certain events.

Study Sites

The study will be conducted at one district each of Nam Dinh and Quang Ninh provinces in Vietnam.

1. Nam Dinh Province:

- The study activities will be conducted at approximately 12 Commune health centers in Vu Ban district.
- Data entry/CRF storage at the Nam Dinh Provincial Preventive Medicine Center (PPMC).
- 2. Quang Ninh Province:
 - The study activities will be conducted at approximately 12 Commune health centers in Quang Yen district.
 - A blood sample will be collected from all infants participating in this study at this site.
 - Data entry/CRF storage at the Quang Ninh CDC.

National Institute of Hygiene and Epidemiology (NIHE) will collaborate with staff of the Commune Health Centers, District Health Center, as well as the staff of the Provincial level for the study. These locations are satellite sites for several vaccine clinical trials conducted in collaboration with NIHE. The staff of the district health center, as well as the staff of the provincial centers in the Nam Dinh province has experience in implementing vaccine trials and observational studies on various infectious diseases and in collaboration with contract research organizations (CROs), and with local and international sponsors. The staff at Quang Ninh and Nam Dinh will be appropriately trained on clinical study procedures before study start.

According to the health system in Vietnam, the district hospitals and their corresponding district health centers; provincial general hospital and CDC/Provincial Preventive Medicine Center are under the same management of Provincial Health Services; so it is easy for coordination of care between them should a serious adverse event occur. The commune health centers conduct routine vaccinations in the community and have the capacity to handle vaccine reactions, in the rare event that these would occur. They also have adequate infrastructure and trained personnel to take care of low grade events. The district hospitals also have a good capacity in terms of both personnel and equipment that meet requirements for medical care, as well as emergency care. These district health centers and their adjacent hospitals are only about 30-40 kilometers (one hour drive) from provincial general hospitals which would be engaged for higher grade adverse events requiring hospitalization or referred events requiring consultation with a specialist. This will assure rapid patient transport and referral to tertiary care hospitals at provincial levels in case such referral is necessary. The study documents will be stored at the provincial level where data entry will occur, and will be moved to the particular commune health center when a study visit is occurring there. The study samples will also be stored at provincial level.

The total time for conduct of the research is approximately 18 months. Recruitment and screening is expected to take approximately 7 months. Once enrolled, each participant will be in the study for approximately 3-4 months [4 (+2) weeks for vaccination and 4 (+2) weeks for follow up).

Schema for randomization

5 STUDY ENROLLMENT AND WITHDRAWAL

5.1 Description of Participants, Source of Participants

Approximately 825 healthy male and female infants, 60-91 days of age will be enrolled in the study from the two provinces in Vietnam.

Dissemination meetings and discussions are ongoing to inform the community leaders on clinical trial background and principles, Rotavirus disease burden/prevention, common Adverse event following Immunizations (AEFIs), overview of vaccine development and any misunderstanding about the vaccines and clinical trials. Post approval of the protocol, commune staff together with population collaborators/village health workers will go household to household and use information from the information sheet of ICF to highlight the broad concepts of the study and eligibility criteria. They will assess interest of potentially eligible families and create a list from their household visits. These people will be invited to an information meeting to learn more about the study and then investigator/designee will go through the consent sheet again with every single participant's parent/LAR and answer the question if any in the private room. Participant's parent/LAR will sign the consent form, if they are interested.

5.1.1 Participant Inclusion Criteria

The following criteria must be met before a participant may be enrolled for participation:

- 1. Healthy infants as established by medical history and clinical examination before entering the study.
- 2. Age: 60-91 days (both days inclusive) at the time of enrollment.
- 3. Parental/LAR ability and willingness to provide written informed consent.
- 4. Parent/LAR who intends to remain in the area with the child during the study period.

5.1.2 Participant Exclusion Criteria

Participants meeting any of the following criteria will be excluded from participation:

- 1. Presence of diarrhea or vomiting in the previous 72 hours or on the day of enrollment (temporary exclusion).
- 2. Presence of fever on the day of enrollment (temporary exclusion).
- 3. Acute disease at the time of enrollment (temporary exclusion).
- 4. Concurrent participation in another clinical trial at any point throughout the entire timeframe for this study.
- 5. Presence of significant malnutrition (weight-for-height z-score < -3SD median)
- 6. Presence of any systemic disorder (cardiovascular, pulmonary, hepatic, renal, gastrointestinal, hematological, endocrine, immunological, dermatological, neurological, cancer, or autoimmune disease) as determined by medical history and / or physical examination which would compromise the participant's health or is likely to result in nonconformance to the protocol.
- 7. History of congenital abdominal disorders, intussusception, or abdominal surgery.
- 8. Known or suspected impairment of immunological function based on medical history and physical examination.
- 9. Household contact with an immunosuppressed individual or pregnant woman.

Confidential

- 10. Prior receipt of rotavirus or an intent to receive this vaccine from outside of the study center during study participation.
- 11. Prior receipt of EPI vaccination during past 7 days or plan to receive them within next 7 days.
- 12. A known sensitivity or allergy to any components of the study vaccine.
- 13. History of allergy to antibiotic kanamycin.
- 14. Clinically detectable significant congenital or genetic defect.
- 15. History of persistent diarrhea (defined as diarrhea that lasts 14 days or longer).
- 16. Receipt of immunoglobulin therapy and / or blood products since birth or planned administration during the study period.
- 17. History of chronic administration (defined as more than 14 days) of immunosuppressants including corticosteroids. Infants on inhaled or topical steroids may be permitted to participate in the study.
- 18. Any medical condition in the parent/LAR or infant which, in the judgment of the Investigator, would interfere with or serves as a contraindication to protocol adherence.

5.1.3 Continued Eligibility Confirmation for subsequent vaccination

The following events constitute absolute contraindications to rotavirus vaccination and all participants should be evaluated for these before administration of second dose of the study vaccine. If any of these events occur during the study, the participant must not receive additional doses of the vaccine but should be appropriately followed up for safety by the Investigator.

- Hypersensitivity reaction following the administration of the study vaccine.
- Any uncorrected congenital malformation of the gastrointestinal tract (such as Meckel's diverticulum) which is diagnosed after the first vaccination and that would predispose for intussusception.
- Infants with any history of intussusception.
- Severe combined immunodeficiency (SCID).
- Detection of one or more of the exclusion criteria during dosing period.

The following events constitute contraindications to administration of the study vaccine at that point in time; if any of these events occur at the time scheduled for vaccination, the participant may be vaccinated at a later date or withdrawn at the discretion of the Investigator.

- Acute disease and / or fever at the time of vaccination.
 - Acute disease is defined as the presence of a moderate or severe illness with or without fever. All vaccines can be administered to persons with a minor illness such as mild upper respiratory infection without fever.
 - Fever is defined as temperature $\geq 37.5^{\circ}$ C (99.5°F) on axillary setting.
- Gastroenteritis within 72 hours preceding the study vaccine administration.

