Table 1: Trial Schema- Schedule of Events

D = day; AE = adverse events; SAE = serious adverse event; Shading represents days of vaccination; V = Visit number.

* The study visits will be planned in advance such that the EPI vaccination days fall either 7 days before or after the study vaccination day. This will allow the participant to receive EPI vaccines in the window allowed by the protocol.

^a Symptom based PE to be performed if screening is being repeated and there is any change in health since last screening.

^bAt Quang Ninh site

^c This includes visit by the health worker to the participant's home on Day 2/58(+1) and 8/64(+2) after each vaccination and a telephone call on Day 5/61 (+2).

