6.6 Concomitant Medications/Treatment

Childhood vaccines as per the Expanded Program for Immunization of the Government of Vietnam [Diphtheria, Tetanus, Pertussis, Haemophilus influenzae type B and Hepatitis B vaccine (DTwP-Hib-HepB) and OPV] and Pneumococcal vaccines will be allowed during the study period but they should not be administered within 7 days before or after study vaccine administration. This is required to avoid any overlap of safety event due to study vaccine and EPI vaccines. The study participants may receive additional doses of OPV as required during special immunization rounds irrespective of the timing of study vaccine.

All non-study vaccines administered during the study will be reported in the "Past and Concomitant Vaccination" section of the CRF.

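### As worded, the last absolute contraindication in Protocol 5.1.3 also bars Dose 2 for an infant found at Visit 2 to have had an EPI vaccine in the previous 7 days, where Section 6.6 only asks for spacing

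*Protocol*

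**What the plan says.** Protocol 5.1.3 has two lists to check before Dose 2.

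- **Absolute list.** Any event on it ends dosing, and the infant is then followed for safety only. The last entry is "Detection of one or more of the exclusion criteria during dosing period".
- **Deferral list.** For these events "the participant may be vaccinated at a later date or withdrawn at the discretion of the Investigator". It names acute disease or fever, and gastroenteritis within 72 hours. EPI receipt is not on it.

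Exclusion criterion 11 in Section 5.1.2 reads "Prior receipt of EPI vaccination during past 7 days or plan to receive them within next 7 days". Criteria 1–3 are marked as temporary exclusions; criterion 11 is not.

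Section 6.6 allows EPI vaccines during the study, with the condition that "they should not be administered within 7 days before or after study vaccine administration". Its reason is "This is required to avoid any overlap of safety event due to study vaccine and EPI vaccines". It adds "The study participants may receive additional doses of OPV as required during special immunization rounds irrespective of the timing of study vaccine".

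On scheduling, Section 4 and the Table 1 footnote (attached to both V1 and V2) say "The study visits will be planned in advance such that the EPI vaccination days fall either 7 days before or after" the study vaccination day. Section 7.2 sets Visit 2 at Day 57 with a window of +14 days, and its step 6 reschedules only for an illness. Section 7.4 lets the investigator give Dose 2 outside the window, and says no blood is taken from an infant who misses a dose.

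In SAP Table A2, row 15 includes criterion-11 infants in PP without review. Row 35 excludes an out-of-window Dose 2, and row 36 excludes a missed dose.

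**The concern.** The bullet carries the enrollment exclusion criteria into the dosing period without exception. One of them, criterion 11, describes something the protocol expects to happen during the study: EPI vaccination goes on around the study visits. If a site finds at Visit 2 that an EPI vaccine was given a few days earlier, the only text in 5.1.3 that covers the case is the absolute bar. The sensible action is to wait a few days, but neither the deferral list nor Section 7.2 step 6 says so.

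Special-round OPV shows the conflict most clearly. Section 6.6 counts OPV among the EPI vaccines and permits special-round doses at any time, but criterion 11 has no matching exception. A permitted event can therefore trigger a permanent bar.

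What is at stake is individual: an infant misses a vaccine dose with no safety reason given in the documents. At Quang Ninh, the only site that contributes to PP, the trial also loses that infant's post-vaccination sample and PP membership.

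**Working it through.** **Step 1. Follow a clash through the text.** An infant attends on Day 57 and had a routine EPI vaccine on Day 53.

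| Provision | Result |
|---|---|
| 5.1.2 criterion 11 | Met; not marked temporary |
| 5.1.3 absolute list, last bullet | No further dose |
| 5.1.3 deferral list | Silent on EPI |
| 7.2 step 6 | Silent (illness only) |
| 6.6 | Spacing rule, for clean safety attribution |
| 7.4 | If Dose 2 is missed, no blood sample |
| SAP Table A2 row 36 | Missed dose: excluded from PP |
| SAP Table A2 row 15 | Criterion 11 met at randomization: kept in PP |

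Row 15 concerns infants randomized despite criterion 11, so it does not directly govern Dose 2. It does show that the SAP does not regard recent EPI receipt as spoiling the immune response. Under the bullet, the same fact at Visit 2 leads to exclusion by way of the missed dose.

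**Step 2. Can the window absorb a deferral?** Visit 2 is at 56 days after Dose 1, which is Day 57. Adding 14 gives Day 71. Let E be the day of the EPI dose. The earliest compliant day is E + 8 if day 7 itself is barred (SAP Table A1 footnote asks for more than 7 days), or E + 7 if day 7 is allowed (Protocol Table 1 footnote).

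| E | E + 7 | E + 8 |
|---|---|---|
| 50 | 57 (no clash) | 58 |
| 51 | 58 | 59 |
| 56 | 63 | 64 |
| 63 | 70 | 71 |
| 64 | 71 | 72 (out of window) |
| 65 | 72 (out of window) | 73 (out of window) |

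For a visit due on Day 57, an EPI dose on Day 50–56 clears by Day 64 at the latest. That is a delay of at most 64 − 57 = 7 days, leaving 71 − 64 = 7 days of window. Any EPI dose given by Day 63 (stricter rule) or Day 64 (looser rule) clears in window. For a visit held on Day 71, no clash clears in window.

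**Step 3. Reproduce the plan's power, then test the effect of losses.** Inputs from Protocol 12.2: 250 and 125 evaluable, SD 0.8 on log10, margin 0.5, one-sided 0.025. A true ratio of 1 is assumed.

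Noncentrality = log10(2) / (0.8 × √(1/250 + 1/125)) = 0.3010 / 0.0876 = 3.435, with 373 degrees of freedom. Power is 92.9%, which agrees with the stated 93%.

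Enrolling 450 with 15% non-evaluable leaves 450 × 0.85 = 382.5, which is 7.5 above the 375 needed, or 7.5/450 = 1.7% of those enrolled. The documents give no clash rate. Assumed losses on top of the 15% give:

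| Assumed extra loss, of 450 | Evaluable | Split | Power |
|---|---|---|---|
| 1% | 378 | 252/126 | 93.1% |
| 3% | 369 | 246/123 | 92.5% |
| 5% | 360 | 240/120 | 91.9% |

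Even an assumed 5% loss costs one percentage point against 92.9%. If the 15% already covers missed doses, it costs less.

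**The case against.** The strongest reply is that nobody would read the bullet this way. Taken word for word it would also make fever or diarrhea at Visit 2 an absolute bar (criteria 1–3), which the deferral list contradicts. On one reading of criterion 10, Dose 1 itself would rule out Dose 2. Criterion 11 was written for enrollment, and Section 6.6 is the more specific text on EPI vaccines after enrollment. Visits are scheduled around EPI days so that, in the protocol's words, "This will allow the participant to receive EPI vaccines in the window allowed by the protocol". Parents are phoned before Visit 2, and Section 7.4 allows even a late Dose 2. Site procedures not included here may fill the gap.

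Much of this stands. The literal result is probably unintended, clashes should be rare, and many sites would defer. A reader might infer that nothing in the protocol points towards waiting; that goes too far, since Sections 4, 6.6 and 7.4 all do. A reader might also infer that infants with fever or gastroenteritis at Visit 2 are permanently barred; the temporary tags and the deferral list show otherwise.

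The reply does not remove the point. For criteria 1–3 the protocol itself supplies the correction; for criterion 11 it supplies none. Scheduling prevents clashes but does not say what to do after one, and Section 7.4 mentions neither EPI vaccines nor an override of the absolute list. A site that sensibly defers and then doses also risks having it recorded as a violation, because SAP Table 7 has a category for dosing when discontinuation criteria were met (although Table A2 row 44 would keep that infant in PP).

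**Conclusion.** The point holds as a minor wording defect. The bullet states a rule that, if followed, withholds Dose 2 after a recent EPI vaccine, at odds with the spacing rule in Section 6.6 and with the treatment of criterion 11 in SAP Table A2 row 15. For a visit due on Day 57, a wait of at most 7 days would resolve the clash inside the window. Late in the window it may not.

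The cost falls on the individual infant and, at Quang Ninh, on one sample and one PP place each time. It would be tempting to infer a threat to power or a biased comparison. The documents support neither: they give no clash rate, power stays at 91.9% under an assumed 5% extra loss, and nothing suggests that clashes would differ between arms. Whether any site would actually withhold a dose is not known from the documents. Confidence is high on the wording conflict and low on how often it would matter.

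**What to change.** 1. In the last absolute bullet of Protocol 5.1.3, insert after the words *exclusion criteria*: *(other than criteria 1–3 and 11)*.
2. Add to the deferral provisions of 5.1.3: *EPI vaccine received within the past 7 days (special-round OPV excepted, see 6.6): defer Dose 2, within the Visit 2 window where possible; this alone is not a reason for withdrawal.* The reference to the window matters because SAP Table A2 row 35 excludes an out-of-window Dose 2 from PP. The last clause matters because the present list allows withdrawal at the investigator's discretion.
3. State that an EPI dose merely planned for the next 7 days is to be moved, so that it neither bars nor delays Dose 2.
4. Extend Section 7.2 step 6 from illness to any temporary contraindication.

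The cost is a few short edits. Because they change dosing contraindications, they should go through as a protocol amendment with the approvals in Section 16.2. The SAP, sample size and database do not change.
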